PTSD, use of antidepressants or anxiolytics will not be an exclusion criterion. The subject may be dropped from the study at the discretion of the research staff.

USE OF SPECIAL/VULNERABLE POPULATION:

For this study, we will be recruiting individuals with PTSD. As individuals with mental illness can be a vulnerable population, we will take particular care to prevent undue coercion, protect the subjects' confidentiality, and obtain informed consent. All subjects will be informed of the purpose of the study, the potential value of the study to society, the lack of value to the subject personally, and potential risks to the subject. It will be explained to the subject that he or she is under no obligation whatsoever to participate, and that if he or she wishes to discontinue involvement at any time during the study he or she is free to do so without penalty. Individuals receiving treatment for PTSD or any medical treatment from the VA will be assured that their treatment will in no way be affected by their choice to participate or not participate, or their choice to withdraw at any time.

STUDY DESIGN:

This study consists of two primary treatment groups: 1) Trauma Management Therapy, comprised of exposure therapy (EXP) and social and emotional rehabilitation (SER) (N = 44), and 2) veterans receiving Prolonged Exposure Therapy (PE), comprised of exposure therapy plus skills-focues group therapy based in Acceptance and Commitment Therapy and informed by Dialectical Behavioral Therapy (EXP + ACT/DBT) (N = 44). All participants will be recruited within the Salem VAMC residential PTSD unit, a 13-bed facility offering residential care for veterans with PTSD. The unit will exclusively offer one of the two arms of treatment (EXP+SER or EXP+ACT/DBT) at any particular time, and the order of offering will be randomized across the year. Thus, assignment to treatment arm will be depend upon the treatment arm being currently offered.

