preprogrammed to play the game. While playing the game, subjects will view stimuli representing their options and choices (e.g., slider bar indicating a choice of \$10). Conditions of certain game variants may include one subject challenging his/her partner at a monetary cost to him/herself. Subjects will be compensated, in part, based on their earnings in the exchange games in order to incentivize performance. The scanner will detect changes in regional cerebral blood flow that accompany neural activity during these tasks. The duration of this task is approximately 30 minutes.

Following completion of the imaging/task session, each participant will be transported via VA vehicle or by their own transportation arrangement from the Human Neuroimaging Laboratory at the Fralin Biomedical Research Institute at Virginia Tech Carilion back to the PTSD residential unit at the Salem VAMC.

Psychotherapy Interventions

Treatment will be conducted by Master's or doctoral-level clinicians at the Salem VAMC. All therapists will be trained and experienced with behavioral treatments for psychological disorders, including PTSD. In addition, therapists will undergo 20 hours of clinical training: 10 hours of didactics and discussion, and 10 hours that will consist of running one mock group through each TMT phase and component, and one individual session where an imaginal scene is constructed and administered to a mock patient. Training will be conducted by TMT experts/creators ([name] & [name]), who will be involved in ongoing supervision and consultation throughout the project. Treatment sessions will follow the manual constructed for TMT and therapists will be supervised in weekly sessions (including the use of recordings of sessions). When problems of adherence or quality are detected, reeducation will occur. We will have adherence data at the end of treatment such that determination of overall adherence can be made.

This study includes two treatment arms, described below. Both treatment arms will be administered across 6 weeks, and the TMT group will include 12 sessions of individualized exposure therapy (EXP); while the PE group will have 12 sessions of individualized exposure therapy. The treatments will also differ, in that Trauma Management Therapy will include 24 sessions of group-based sessions targeting social and emotional rehabilitation (SER), while the control condition will include 24 sessions of skills-focused group therapy (ACT/DBT).

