Our goal is to have 44 subjects in each of the two treatment groups complete this study over the course of four years. From our past experience conducting studies of this complexity with specific inclusion/exclusion criteria, we anticipate needing to enroll 1.5 subjects to achieve 1 subject who meets criteria and finishes the study. Thus, we multiplied our target of 88 subjects by 1.5 to reach our total sample size of **132**.

PROVISIONS FOR MANAGING & REPORTING ADVERSE EVENTS:

During all phases of the study, a doctorate-level clinician will be available for consultation and to help manage any negative reactions that occur in response to the neuroimaging sessions. All study staff working with the patients will be trained in suicide risk assessment, basic suicidal crisis intervention skills, and the study's safety protocol.

If patients exhibit symptoms of significant distress or anxiety at any time during their participation in study procedures at FBRI, they will be guided through clinical techniques to help them regulate their distress. Their session may be terminated if deemed appropriate. If it is determined that they are expressing suicidal/homicidal ideation or thoughts of self-harm or harm to others, clinically

trained staff will work with the veteran to reduce distress and/or acute suicide or homicide risk. When the veteran feels calm and is determined by staff to not be an imminent risk to self or others, they will be escorted back to the residential unit by a trained research staff member via the VA vehicle. If a veteran has driven or ridden in a private vehicle to the appointment and the veteran is deemed stable and safe by staff, they may be allowed to drive their vehicle back to the Salem VA and check in to the residential unit. If at any time clinical staff determine that the Veteran is an imminent risk to self or others and/or not safe to independently drive or ride in a private vehicle, the Veteran will be transported via the VA vehicle or ambulance, whichever is clinically indicated. Study personnel will remain with patients determined to be an imminent risk to self or others until direct hand off to a VA clinician or EMS response is possible.

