JUNE 1, 2023

EFFICACY AND NEURAL MEDIATORS OF
RESPONSE TO TRAUMA MANAGEMENT
THERAPY FOR PTSD
NCT03449576

Analysis of primary clinical outcome hypothesis for D2354-R “Efficacy and Neural Mediators of Response to Trauma Management Therapy for PTSD”

A regression approach was used to test the effect of treatment type (TMT, EXP+EDU) on both primary (CAPS-5 and SAS-SR) and secondary (PCL-5, AQ, ITS) outcome measures across Time (pre-treatment, post-treatment). The Time x Treatment interaction was be used to test whether TMT improves outcomes relative to EXP+EDU, and age was entered as a co-variate as the two treatment arms differed in age at baseline.

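### Arm follows the calendar period of admission, but the SAP model has no Year x Time or offering-period term, so between-year drift in pre-to-post change can enter the treatment estimate

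*SAP*

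**What the plan says.** **Assignment (Protocol, Study Design).** "The unit will exclusively offer one of the two arms of treatment (EXP+SER or EXP+ACT/DBT) at any particular time"; "the order of offering will be randomized across the year"; and "assignment to treatment arm will be depend upon the treatment arm being currently offered". The section gives no length or number of offering periods, no restriction within or between years, and no number to be enrolled per arm per year.

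**Duration and size (Protocol, Sample Size).** The target is to have "44 subjects in each of the two treatment groups complete this study over the course of four years".

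**Analysis (SAP).** The regression covers the primary outcomes (CAPS-5, SAS-SR) and the secondary outcomes (PCL-5, AQ, ITS) at two time points, before and after treatment. "The Time x Treatment interaction was be used to test whether TMT improves outcomes relative to EXP+EDU". Age is the only covariate, included because the arms differed in age at baseline. No year, period, block or cohort term is named, and nothing is said about correlation among veterans treated in the same period. The SAP's label for the comparator differs from the protocol's; it is called control below.

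**The concern.** Treatment is tied to calendar time by design, so an analysis that ignores calendar time may mix the two. The Time x Treatment term is the difference between arms in mean pre-to-post change. If veterans admitted in some years improve more than those admitted in others, and one arm has more of its veterans in those years, the pooled contrast partly compares years. That could imitate a benefit of TMT or hide one.

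Drift in change is plausible. Over four years therapists gain experience and the referred population can shift. The Consent Procedures section also records a COVID-19 change: pretreatment interviews moved to telephone or video and could precede admission by up to two months before being repeated. A change that affects only the baseline measurement alters pre-to-post change itself.

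Precision is also at stake. Even with identical enrolment shares, between-year variation in change that is left out of the model inflates the residual.

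**Working it through.** **The plan's own figure.** 44 x 2 = 88 completers; 88 x 1.5 = 132 enrolled, as the protocol states. The documents give no alpha, power, effect size or SD, so 44 per arm cannot be derived from them. For scale, 44 per arm detects about 0.60 SD with 80% power at two-sided 5% (assumed).

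**Formula.** With complete pre/post pairs:

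bias = sum over years of (TMT share in year − control share in year) x mean change in that year.

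Three consequences were confirmed by noise-free least-squares fits:

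- A drift in level that is the same before and after treatment (0.2 SD per year tried) gives bias 0.000 in every split, because it cancels from the interaction.
- A year main effect alone leaves the estimate unchanged.
- Year x Time brings the bias to 0.000 in every scenario tried.

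**Assumed inputs for what follows.** 44 per arm, change-score SD 1, no true effect, veterans independent unless stated. All drifts and yearly splits are assumptions.

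**One poor year (0.5 SD less improvement in year 3).**

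- TMT 13/13/5/13, control 9/9/17/9: bias = (17 − 5)/44 x 0.5 = 0.136 SD. Against SE = sqrt(2/44) = 0.213 that is 0.64 SE. Simulated false-positive rate about 8% to 9%; with Year x Time, 4.4% to 5.1%. The SE is 0.217 pooled and 0.224 with Year x Time, about 3% larger.
- TMT 12/12/8/12, control 10/10/14/10: bias = (14 − 8)/44 x 0.5 = 0.068 SD; false-positive rate between 5% and 6%.

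**Linear drift in change.** Bias = difference in mean enrolment year x drift per year.

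| TMT by year | Control by year | Difference in mean year | Bias at 0.1 / 0.2 SD per year | False-positive rate |
|---|---|---|---|---|
| 11,11,11,11 | 11,11,11,11 | 0 | 0 / 0 | 5.1% / 4.6% |
| 9,10,12,13 | 13,12,10,9 | 14/44 = 0.318 | 0.032 / 0.064 | 5.1% / 5.3% |
| 7,9,13,15 | 15,13,9,7 | 28/44 = 0.636 | 0.064 / 0.127 | 5.9% / 8.6% |
| 4,8,14,18 | 18,14,8,4 | 48/44 = 1.091 | 0.109 / 0.218 | 7.7% / 16.5% |
| 15,7,7,15 | 7,15,15,7 | 0 | 0 / 0 | 4.8% / 4.5% |

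The last row has very uneven shares but no bias, because the imbalance does not line up with the drift.

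**What chance ordering would give.** Assume 32 six-week periods, eight a year. If arms are balanced within each year, the difference in mean enrolment year stays within 0.47 in 95% of orderings, so bias stays within about 0.05 to 0.09 SD at 0.1 to 0.2 SD drift per year. If the order is unrestricted, the limits are 0.93 and about 0.09 to 0.19 SD.

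**Precision with equal shares.** With 11 per arm per year and year effects 0.3, −0.3, −0.5 and 0.2 SD, the between-year variance is 0.47/4 − 0.075² = 0.112. Pooled SE = sqrt(2 x 1.112/44) = 0.225; with Year x Time it is sqrt(2/44) = 0.213. Power for a 0.5 SD effect rises from about 60% to 64%.

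**Correlation within offering period.** The 5% rate after adding Year x Time assumes independent veterans. With within-period correlation in change of 0.05 to 0.10 (assumed), that model rejected about 11% to 18% of the time with eight periods and 6% to 7% with 32. The design effect shows why: with 88/8 = 11 veterans per period it is 1 + 10 x 0.05 = 1.5, or 2.0 at 0.10; with 88/32 = 2.75 per period it is 1.09 to 1.18.

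**The case against.** The strongest reply is that the protocol gives no enrolment by year and no evidence of drift, and that randomising the order within a year would tend to put both arms in every year, which limits imbalance. The 0.136 SD case needs 5 versus 17 veterans in exactly the year that goes badly; milder splits leave the error rate near 5%. The precision gain likewise depends on assumed year effects spanning 0.8 SD. All of this stands, and it is why no single magnitude can be asserted.

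Two further objections also stand. First, year as the formal randomisation block is a reasonable inference from the wording about the order being randomised across the year, but it is not stated; nor does four years necessarily mean four calendar years. Second, Year x Time does not deal with correlation within offering periods or with change inside a year, so offered alone it would be an incomplete remedy.

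The SAP is also written in the past tense, so the analysis appears to have been run. Replacing the stated model now would be a post hoc switch. That limits how the added analysis is reported. It does not remove the reason for doing it, because assignment was restricted by time and the model does not reflect this.

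**Conclusion.** The gap is real: a design that assigns by calendar period is analysed with no term for calendar time. Bias arises only from drift in pre-to-post change, and only when it lines up with unequal enrolment shares by year. Under the assumptions shown it runs from 0 to about 0.14 SD, up to 0.22 SD in the most extreme split tried, and is smaller if both arms ran in every year. With equal shares the cost is precision only.

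A reader might infer that any difference between years biases the result, or that any unequal split does. Neither follows: level drift common to both time points cancels when pairs are complete, though it could enter if post-treatment data are missing unevenly and unpaired records are used, and unequal shares unrelated to the drift do no harm. A reader might also infer that the reported estimate is in fact biased, or that adding a year term is enough. The documents cannot show the first. The second fails because a main effect changes nothing, and Year x Time alone does not hold the 5% error rate if veterans in the same period are correlated.

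**What to change.** 1. Tabulate the numbers enrolled and analysed per arm by year and by offering period, and state how the order of offering was randomised.
2. Add year of admission and Year x Time as fixed effects to the CAPS-5, SAS-SR, PCL-5, AQ and ITS models, and read Time x Treatment as the within-year arm difference. Define year to match the schedule within which the order was drawn.
3. Allow for correlation within offering period, for example by a period-level random effect on change or by cluster-robust errors with a small-sample correction.
4. Report this beside the original pooled model, labelled as added after the original analysis.

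**Cost.** A short SAP addition and a rerun, with no new data. Four years use about 4 − 1 = 3 degrees of freedom for Year x Time, and the SE rises slightly if the arms are very uneven by year (about 3% in the 13/13/5/13 case). If there were few offering periods, the period-level test will have few degrees of freedom: 8 − 4 − 1 = 3 with eight periods, against 32 − 4 − 1 = 27 with 32. A wide interval in that case would reflect how little independent information the schedule supplied.

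### Entering age beside Time x Treatment does not, as written, adjust the primary test for the age imbalance; an Age x Time term is needed and is not stated

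*SAP*

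**What the plan says.** The SAP is one paragraph, headed as the analysis of the primary clinical outcome hypothesis. It describes a regression of each outcome over two time points, before and after treatment, applied to "both primary (CAPS-5 and SAS-SR) and secondary (PCL-5, AQ, ITS) outcome measures". The treatment test is named: "The Time x Treatment interaction was be used to test whether TMT improves outcomes relative to EXP+EDU". Age is then added, with a reason: "age was entered as a co-variate as the two treatment arms differed in age at baseline".

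The SAP gives no equation, Age x Time term, participant effect or covariance structure, and no rule for missing post-treatment scores. The protocol has no analysis section and does not mention adjustment for age.

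On allocation, the protocol (Study Design) says the residential unit runs one arm at a time, in randomized order: "Thus, assignment to treatment arm will be depend upon the treatment arm being currently offered".

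**The concern.** The reason given for the age term is the imbalance between arms, so the term is meant to protect the treatment comparison. Entered in the ordinary way as a covariate, age adjusts the level of the outcome. The treatment test does not use level. It uses change from pre to post, and a quantity that is constant within a person drops out of that person's change.

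If older and younger veterans improve by different amounts, part of any Time x Treatment effect on CAPS-5 or SAS-SR would be an age effect, yet a reader would take it as age-adjusted. Allocation makes this more than a formality: because arms follow treatment periods, a difference in age between the groups admitted in those periods passes straight into the arms. The SAP confirms that an age difference arose.

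**Working it through.** **The plan's own figure.** The only computable figure in the documents is the enrolment total: 2 x 44 x 1.5 = 132 (Protocol, Sample Size). It reproduces, and this point does not depend on it.

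**Algebra.** For veteran *i* in arm *g* (0 or 1) with age *A*, at time *t* (0 = pre, 1 = post), the model as written is

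y = b0 + b1 t + b2 g + b3 (t x g) + b4 A + error.

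Subtracting pre from post gives

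post - pre = b1 + b3 g + error.

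The b4 A term has gone. With complete pairs, the estimate of b3 is the difference between arms in mean change, whether or not age is in the model. Adding b5 (A x t) gives

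post - pre = b1 + b3 g + b5 A + error,

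which is the regression of change on treatment and age. Only this version adjusts b3 for age.

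**Numerical check, complete pairs.** Over 300 simulated data sets, random-intercept and ordinary least-squares fits with and without the age main effect differed in the interaction by at most 4e-15. The Age x Time model matched the change-score regression to 2e-15. In a separate example (age gap 6 years, age SD 11, outcome SD 10, correlation 0.5, age slope on change 0.2 points per year, no true effect, all assumed), the interaction was 1.9277 without age, 1.9277 with age, and -0.40 with Age x Time.

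**Size of the bias.** Inputs: 44 per arm is the completion target in Protocol, Sample Size. The rest are assumptions: no treatment effect, score SD 1, pre-post correlation rho, within-arm age SD 1, age gap *d*, and slope *s* of change on age in SD units.

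- Bias without Age x Time = d x s. For example, 0.5 x 0.3 = 0.15.
- Variance of change within arm, taking the score SD as that at a given age = 2(1 - rho) + s^2. At rho 0.5 and s 0.3: 1 + 0.09 = 1.09.
- Standard error of the difference = sqrt(2 x 1.09 / 44) = 0.223.
- Shift = 0.15 / 0.223 = 0.67 standard errors, so by the normal approximation the two-sided 5% test rejects about 10.3% of the time.

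Simulation, 6000 runs per setting, without Age x Time:

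| Age gap (SD) | Slope | rho | Bias (SD) | Type I error |
|---|---|---|---|---|
| 0.5 | 0 | 0.5 | 0 | 5.2% |
| 0.5 | 0.1 | 0.5 | 0.05 | 6.2% |
| 0.5 | 0.2 | 0.5 | 0.10 | 8.1% |
| 0.5 | 0.3 | 0.5 | 0.15 | 10.4% |
| 0.25 | 0.3 | 0.5 | 0.08 | 6.4% |
| 0.75 | 0.3 | 0.5 | 0.22 | 17.2% |
| 0.5 | 0.3 | 0.3 | 0.15 | 9.0% |
| 0.5 | 0.3 | 0.7 | 0.15 | 13.8% |

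With Age x Time, bias was below 0.01 SD and type I error was 4.6% to 5.6% in all 18 settings run.

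**Missing post-treatment scores.** The exact cancellation needs complete pairs. As an upper reading of the protocol's enrolment factor ("we anticipate needing to enroll 1.5 subjects to achieve 1 subject who meets criteria and finishes the study"), one third of post scores were removed at random (gap 0.5, slope 0.3). The mean interaction was 0.152 without age, 0.152 with the age main effect and 0.001 with Age x Time. The age main effect moved single estimates by 0.009 SD on average and 0.063 at most.

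**Precision cost of Age x Time when age is unrelated to change.** The variance ratio is roughly 1 + d^2/4, giving 1.016, 1.063 and 1.141 at gaps of 0.25, 0.5 and 0.75 SD. Chance variation in the age gap adds about (2/44)/4 = 0.011. Simulated ratios were 1.036, 1.074 and 1.151. A separate run at 0.5 SD gave 1.095.

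**The case against.** The strongest reply is that the SAP never says age entered as a main effect only. It speaks of a regression and a covariate, in two sentences of summary. Some repeated-measures routines cross covariates with Time automatically, and a change-score regression with age would also adjust properly. The fault may therefore lie in the reporting and not in the analysis. This stands as a limit on the claim, which concerns the plan as written. It does not remove the point: the ordinary reading is a main effect, and a reader cannot tell whether the adjustment did anything.

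Second, the harm is conditional. The age gap and slope are assumed, and the 17.2% pairs the largest gap with the largest slope tried. The error rates also hold the age gap fixed in size and direction, whereas the order of offering was randomized, so they are not the design's overall error rates. That is correct, and the figures should be read as illustrations. Conditioning on a gap is still proper, because the SAP reports one and makes it the reason for adjusting.

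Third, with dropout one trial's estimate can move more than the average suggests: up to 0.8 to 1.1 points on an SD of 10 in the separate set of simulations. This is true, but the movement has no consistent direction and leaves the mean bias in place. The one-third rate also covers ineligible as well as non-completing veterans, so it probably overstates the missing data.

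Fourth, whether ANCOVA should be primary or only a sensitivity analysis is debatable. That choice is optional here and the point does not depend on it.

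**Conclusion.** The concern holds for the SAP as written. That an age main effect cannot adjust a two-time-point Time x Treatment contrast with complete pairs is algebra and needs no assumed figure. Whether this trial's result is affected depends on two quantities the documents do not give: the age difference between arms and the relation of age to change. If that relation is nil, there is no bias. Over the assumed ranges with a non-zero slope at 44 per arm, the settings tabulated put bias at 0.05 to 0.22 SD and type I error at 6.2% to 17.2%. It should be fixed, since it bears on both primary outcomes. Confidence is medium, because the model actually fitted may already have contained Age x Time.

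**What to change.** - Write out the model for each outcome: a repeated-measures model with a participant effect and terms for Time, Treatment, Time x Treatment, Age and Age x Time. With complete pairs, regressing change on treatment and age is equivalent.
- If the software already included Age x Time, say so; the matter then closes with one sentence.
- Report the age difference between arms, and give the Time x Treatment estimate without age next to the adjusted one, because age was chosen from the observed imbalance.
- ANCOVA (post score on treatment, baseline score and age) may be added as a sensitivity analysis. With arms assigned by period, it can be biased if they differ in stable baseline severity.

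The cost is one extra term, a short addition to the SAP and a re-run on data already collected, plus the few extra reported figures above. The precision cost is about 7% in variance at a 0.5 SD age gap if age is unrelated to change (4% at 0.25 SD, 15% at 0.75 SD). Because the SAP is written in the past tense, the model as run should stay on display and the corrected one be labelled as added later.
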